## 7.5 ECG

Electrocardiogram (ECG) measures will be collected at screening, Baseline and the Day 2 visit. The number and percent of ECG findings of normal; abnormal, not clinically significant; and abnormal, clinically significant will be presented for each scheduled measurement. The following ECG interval measurements will be summarized by presenting descriptive statistics of actual values and change from baseline values at each scheduled visit:

- PR Interval (ms)
- QRS Duration (ms)
- Ventricular Rate (bpm)
- QT Interval (ms)
- RR Interval (ms)
- QTcF Interval (ms)

Listings will include measurements at each scheduled visit as well as any unscheduled visits.

## 7.6 Physical Examination

The number and percentage of subjects with physical examination findings of normal and abnormal at each visit will be summarized and presented for each body system. A listing of physical examination findings will also be provided.

#### 7.7 C-SSRS

The Columbia-Suicide Severity Rating Scale (C-SSRS) assesses a subject's suicidal ideation (severity and intensity) and behavior. The C-SSRS has 11 categories: 5 subtypes of suicidal

#### CONFIDENTIAL

ideation, 5 subtypes of suicidal behavior and 1 subtype of self-injurious behavior without suicidal intent. All responses are binary (yes/no).

The number and percent of subjects answering 'Yes' to each of the 11 categories will be provided for each scheduled time point. No statistical comparisons between treatment groups will be performed. A by-subject data listing will be provided.

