8.4.2. Columbia-Suicide Severity Rating Scale (C-SSRS)

The C-SSRS will be used to assess the subject's suicidal ideation (severity and intensity) and behavior during screening and throughout the study. The C-SSRS Baseline/Screening Version will be administered by the Investigator or designee at Screening (Visit 1) and will use recall periods of lifetime and over the past 3 months. The C-SSRS – SLV Version will be used at all other visits where the C-SSRS is to be administered, as described in the Schedule of Activities (Table 2).

For both versions, if the subject provides a "Yes" response in the Suicidal Behavior sections of the C-SSRS for Actual Attempt, Interrupted Attempt or Aborted Attempt, the site should inquire about the approximate date when the event occurred and record this in the source document and eCRF.

The C-SSRS is a validated outcome assessment tool that evaluates suicidal ideation or behavior defined within 11 categories (5 subtypes of suicidal ideation, 5 subtypes of suicidal behavior, and 1 subtype of self-injurious behavior without suicidal intent) with binary responses (yes/no) (Posner 2011).

Any positive findings or changes in the subject's suicidal ideation/behavior that are revealed by the subject's responses to the C-SSRS should be handled in accordance with local standard of care and at the Investigator's discretion. The Investigator may consult with the Sponsor's Medical Monitor on any questions related to treatment and/or follow-up of such findings.

The C-SSRS may be administered by certified site raters. DSMs may administer the C-SSRS if qualified.

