## 4.7 Data Derivations and Transformations

The following derivations will be used in this study:

Study Day:

- Equal to (date of assessment date of first dose + 1) for assessments done on or after date of first dose
- Equal to (date of assessment date of first dose) for assessments before date of first dose

Baseline Observation: the last non-missing value prior to first study drug administration.

Duration: end date – start date +1; measured in days.

Change from Baseline: post-baseline value - baseline value

Percent Change from Baseline: (post-baseline value - baseline value) / baseline value x 100

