#### 7 SAFETY ANALYSIS

Safety assessments include adverse events, laboratory parameters, vital signs, electrocardiograms, physical exams and the Columbia Suicide Severity Rating Scale (C-SSRS). All safety summaries will be conducted using the safety (SAF) population and will be presented by treatment group. No formal hypothesis testing will be performed to compare differences between treatment groups.

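### By-visit C-SSRS percentages cover recall periods from about half a day to 30 days (lifetime at Screening), and no planned table counts subjects per arm with any post-dose, or new or worsened, ideation or behaviour

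*SAP*

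**What the plan says.** SAP 7.7 sets out one C-SSRS summary: the "number and percent of subjects answering 'Yes' to each of the 11 categories will be provided" for each scheduled time point. It adds a by-subject listing and states: "No statistical comparisons between treatment groups will be performed". SAP 7 applies the general safety rule: "All safety summaries will be conducted using the safety (SAF) population and will be presented by treatment group".

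Protocol 8.4.2 fixes the recall. The Baseline/Screening form, used at Visit 1, "will use recall periods of lifetime and over the past 3 months". After that, the "SLV Version will be used at all other visits where the C-SSRS is to be administered". The Schedule of Activities (Protocol Table 2) places the Since Last Visit (SLV) form at Baseline, Visits 3A and 3B, Day 2 and Weeks 1, 2, 4, 8 and 12.

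SAP 7.7 does not mention recall periods, does not say which Screening recall is tabulated, and defines no cumulative or treatment-emergent C-SSRS summary. C-SSRS is a named safety endpoint in Protocol section 3.

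**The concern.** An SLV form covers whatever time has passed since the previous form. The rows of the planned table therefore describe periods of very different length under one percentage heading. Someone reading down an arm could take a low figure around dosing and a higher one at Weeks 8 and 12 as a change in risk, when the longer rows have simply had more time to collect events.

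The second problem does not depend on any assumed rate. The safety question for a single-dose trial is how many subjects in each arm had suicidal ideation or behaviour after dosing, and in how many it was new or worse. A table of separate visit counts cannot answer that, because it does not show whether the same subject answered Yes at several visits.

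**Working it through.** **Inputs.** Visit days and windows come from Protocol Table 2. Its footnote places the Visit 3B form at least 12 hours after dosing and before release. SAP section 9 gives 36 subjects per arm. Neither document gives a C-SSRS rate, so there is no plan figure to reproduce, and the rates below are assumptions.

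**Step 1: recall length.** Recall = day of this form minus day of the previous form. For example, Week 8 is 57 − 29 = 28 days; with windows, the range is 52 − 32 = 20 to 62 − 26 = 36.

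**Step 2: what unchanged risk would look like.** Assume 5% of subjects have an event per 30 days. Then λ = −ln(0.95)/30 = 0.00171 per day.
- All events episodic: P(Yes) = 1 − exp(−λt).
- Half persistent: P(Yes) = 2.5% + 97.5% × [1 − exp(−λt/2)].
- All persistent: 5% at every visit.

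| Form | Recall, days (range) | All episodic | Half persistent | All persistent |
|---|---|---|---|---|
| Baseline | up to 30 | 5.0% | 5.0% | 5% |
| Visit 3A | 3 (1–5) | 0.5% | 2.8% | 5% |
| Visit 3B | about 0.5 | 0.09% | 2.5% | 5% |
| Day 2 | about 0.5 | 0.09% | 2.5% | 5% |
| Week 1 | 6 (5–7) | 1.0% | 3.0% | 5% |
| Week 2 | 7 (3–11) | 1.2% | 3.1% | 5% |
| Week 4 | 14 (8–20) | 2.4% | 3.7% | 5% |
| Week 8 | 28 (20–36) | 4.7% | 4.8% | 5% |
| Week 12 | 28 (18–38) | 4.7% | 4.8% | 5% |

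The Baseline row uses its 30-day maximum. In the all-episodic case Week 8 exceeds Visit 3B about 55-fold. Over assumed 30-day rates from 1% to 20%, the ratio runs from about 56 down to 51. In an arm of 36, the expected number of Yes answers is 36 × 0.00085 = 0.03 at Visit 3B and 36 × 0.0467 = 1.7 at Week 8. The chance of at least one is 1 − (1 − 0.00085)^36 = 3% and 1 − (1 − 0.0467)^36 = 82%.

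**Step 3: can visit counts give subjects?** For one category, the number of subjects with any post-dose Yes lies between the largest visit count and the sum of the visit counts. One Yes at each of four visits could be one subject (1/36 = 2.8%) or four (4/36 = 11.1%).

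The same assumed rate shows the point from the other side. The seven post-dose recalls sum to 0.5 + 0.5 + 6 + 7 + 14 + 28 + 28 = 84 days.
- All episodic: the visit percentages sum to about 14.1%, or 36 × 0.141 = 5.1 Yes answers, from 36 × [1 − exp(−84λ)] = 36 × 0.134 = 4.8 subjects.
- All persistent: 7 × 1.8 = 12.6 Yes answers, from 36 × 0.05 = 1.8 subjects.

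The arm with more Yes answers has fewer affected subjects, and the planned table alone does not identify which situation applies.

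**Step 4: does another output supply the count?** SAP 7.2.6 counts each subject once across the study, but only for adverse events. Under Protocol 9.4, clinician-reported measures are not a primary route for collecting adverse events, and Protocol 8.4.2 leaves positive C-SSRS findings to local standard of care and the Investigator's discretion. The SAP addendum (4.1.2) adds adverse-event tables split at dosing day and nothing on C-SSRS.

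**The case against.** Much of the case on the other side stands.

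- **The dip and rise are not inevitable.** A reader might infer that the display produces a fall at dosing and a rise afterwards whatever the truth. That needs episodic events. The documents give neither a rate nor a persistence pattern, and the right-hand columns above show the effect shrinking and then vanishing.
- **Recall is not different at every visit.** Visit 3B and Day 2 match, Weeks 8 and 12 match, and Weeks 1 and 2 nearly do.
- **Recall is not the only cause of a low pre-dose figure.** Protocol 8.1.4 makes a subject with a Yes on ideation item 4 or 5 at Visit 3A ineligible for dosing, so that subject does not enter the Safety Set.
- **Arms are compared fairly at a given visit.** All five follow one schedule, so a reader who inferred recall bias between dose and placebo would be wrong.
- **No change-from-baseline analysis of C-SSRS is planned.** The general SAP 4.7 rule takes "the last non-missing value prior to first study drug administration", which for C-SSRS is the Visit 3A form with 1–5 days of recall. A reader might infer that almost any later Yes will be classed as new. SAP 7.7 plans no such classification.
- **Suicidality is not wholly hidden.** The listing identifies every subject with a Yes, and events that the site judges to be adverse events reach the adverse-event tables by arm.

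What does not answer the point: a listing is not a summary by arm, and adverse-event recording depends on investigator judgement and does not follow the 11 C-SSRS categories. At the short-recall visits a fair comparison between arms is also nearly empty: on the episodic assumption, an arm has a 3% chance of showing any Yes at Visit 3B. This is not true of every visit, as the 82% at Week 8 shows.

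**Conclusion.** The point holds as a limitation of descriptive safety reporting. From the schedule alone, recall ranges from about 0.5 day to 28 days after dosing, and up to 30 days at Baseline, so percentages within an arm are not comparable across visits. Any artificial dip and rise is conditional: about 51- to 56-fold between Visit 3B and Week 8 if all events are episodic, roughly 2.5% to 4.8% if half of an assumed 5% is persistent, and none if all is persistent.

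The missing subject-level count by arm rests on no assumption about rates. It follows from the planned display and from the absence of any other table giving it. Nothing here touches alpha, power or the primary analysis, and no data are lost.

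**What to change.** In SAP 7.7 add, by arm in the Safety Set:

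1. Subjects with any Yes from Visit 3B through Week 12, for each of the 11 categories.
2. Treatment-emergent ideation or behaviour, meaning new or worse than a stated pre-dose reference: Screening past-3-months plus the Baseline and Visit 3A SLV forms.

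State the limit of that reference. It can span about 91 + 30 + 5 = 126 days against 84 days of follow-up, which makes new harder to meet. On the assumed episodic 5% per 30 days, 1 − exp(−126λ) = 19.4% would have a pre-dose Yes, against 13.4% over 84 days. It should not be described as a like-for-like comparison.

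In the by-visit table, show Screening lifetime and past-3-months separately, label every row with its recall period, and state that trends across visits will not be interpreted.

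The cost is SAP wording and one additional by-arm table from data already collected. No visit, form or clinical rule changes.

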## 8 INTERIM ANALYSIS AND CHANGES FROM PROTOCOL

No formal interim analysis was planned for the study.

During the conduct of the study, a Sponsor decision was made to perform the analysis of the primary endpoint when all enrolled subjects reached their Week 4 visit. The approximately 180 subjects will provide adequate power to determine the dose-response relationship as defined in the primary objective of the study. No further subjects will be enrolled, and the study will continue to its normal conclusion.

This 'Top-Line' analysis will be the final analysis for the HAM-A primary endpoint at Week 4, HAM-A response and remission through Week 4, HAM-A change from baseline through Week 4, MADRS change from baseline through Week 4 and CGI-S through Week 4. Preliminary analysis of Subject Disposition, and Adverse Events will be provided as well. As this will be the final analysis for the select efficacy endpoints through Week 4, this is not considered an interim analysis and no adjustment to the overall alpha level of the trial is needed.

At the time of analysis, data for the select efficacy analyses through Week 4 will be cleaned and locked in the clinical trial database according to the Data Management Plan. Supporting data for the preliminary analyses will be cleaned and frozen, and a snapshot of the database taken.

A pre-defined unblinded statistician and programmer, not involved with the conduct of the study, will perform this analysis. The Study team will remain blinded through the completion of the study. The topline results for the primary endpoint will not be available to the Study Team or externally until the final subject has completed their last visit assessment.

The remaining secondary efficacy analyses and final safety analyses will be conducted at the completion of the trial.

## 9 SAMPLE SIZE AND POWER CALCULATIONS

A total sample of 180 subjects, 36 per arm, is required to ensure a mean power >87% for an MCP-Mod Analysis rejecting the hypothesis of a constant dose-response curve using the multiple comparisons procedure (MCP), assuming a null placebo response, a maximum standardized effect of 0.6 within the doses range, and a common standard deviation within the dose arms, if a studywise one-sided type-1 error rate <0.05 is required.

The analysis assumes 4 doses of active medication (25, 50, 100 and 200  $\mu$ g freebase-equivalent) and placebo. The required sample size for each arm is 36 subjects.

The R package Dose Finding (https://CRAN.R-project.org/package=DoseFinding) has been used to estimate the sample size and corresponding power. The power for each model is estimated as shown Table 6.

Table 6	Power by Mode

Model	Power (%)
Sigmoid Emax (ED50, hill)	
10, 1	84.5
100, 5	90.7
100, 10	91.0
150, 10	89.9
Emax (D50 = 100)	83.2
Linear	85.0

## **11 APPENDICES**

## 11.1 Appendix A

## Table 11-1MMED008 Schedule of Activities

STUDY PERIOD	Optional Prescreen	SCREENING	BASELINE & DOSING					FOLLOW-UP			
Visit	Prescreen	Screening*	Baseline	D: Randomiz Dosing S	ay 1 ation (3A) & ession (3B)	Day 2	Week 1	Week 2	Week 4	Week 8	Week 12 (or Early WD)/EOS
Visit Number	N/A	1	2	3A	3B	4	5	6	7	8	9
Timing or Permitted Window	none	Up to 30 days prior to Baseline	1-5 days prior to Day 1 b, c	Pre- dose	Dosing & post- dose	l day after dosing	Day 8 ±1 day	Day 15 ± 3 days	Day 29 ± 3 days	Day 57 ± 5 days	Day 85 ± 5 days
Administrative Procedures	-	-	-				-	-			
Prescreen Informed Consent	X										
Informed consent		X			!		l				
Demographics	X	X									
Eligibility assessment		Х	Х	X							
Medical psychiatric and medication history d	x	Medical/psy medical/psychiatr	Medical/psychiatric and medication history will be collected via interview at Screening [Visit 1] if information about the medical/psychiatric and medication history is learned during the course of the study, this will also be recorded, even if first lear after Screening [Visit 1].					oout the first learned			
Medication taper (if applicable)		х									
Concomitant medication & non-medicinal therapy collection	x	Medications/non-1 whether th	medicinal therapies he subject is on the 1 Medications/thera	used at Ba nedication pies stopp	aseline [Vis n/therapy at ved prior to	it 2] or any the time of Baseline [V	time after, [the site visi [isit 2] are i	including th it, will be rea recorded in i	ose taken bet corded in the nedication h	ween visits, designated istory.	regardless of CRF.
Randomization				X							
Clinical Procedures/Assessme	ents										
Physical examination		X				X					X
Neuropsychiatric examination			х			x	х	х	х	х	x
Vital signs e (BP, heart rate, respiration rate, temperature)		x	х	Xf	x	х	х	х	х	х	x
Weight	Xg	X									
Height	Xg	X									
BMI	X	X									
12-lead safety ECG		Х	Х			Х					
Adverse event collection		AEs are evaluated between signing o Events occ	s are evaluated from the time informed consent is given until completion of the study and captured at each visit. Events occurring ween signing of the informed consent form and dosing with study drug will be recorded on the medical history page of the eCRF. Events occurring from the time study drug is administered through EOS will be recorded on the AE page of the eCRF.								

STUDY PERIOD	Optional Prescreen	SCREENING	BASELINE	E & DOSING FOLLOW-UP							
Visit	Prescreen	Screening*	Baseline	Da Randomiza Dosing S	ay 1 ation (3A) & ession (3B)	Day 2	Week 1	Week 2	Week 4	Week 8	Week 12 (or Early WD)/EOS
Visit Number	N/A	1	2	3A	3B	4	5	6	7	8	9
Timing or Permitted Window	none	Up to 30 days prior to Baseline	1-5 days prior to Day 1 b, c	Pre- dose	Dosing & post- dose	l day after dosing	Day 8 ±1 day	Day 15 ± 3 days	Day 29 ± 3 days	Day 57 ± 5 days	Day 85 ± 5 days
Laboratory Procedures/Asses	ssment										
Blood sample collection for biobanking (DNA)				If the	e subject giv sample once	ves informe e during the	d consent to study, prej	X provide a p ferably at Da	harmacogen 1y 1/Random	omic sample ization [Visi	, collect a t 3A].
Blood sample collection for safety laboratory assessments		x	x			x	Opt h	Opt h	x	x	x
Urine pregnancy test (if applicable)		х		х			x	x	х	х	x
Serum pregnancy test (if applicable)			х								
Screening and Efficacy Quest	tionnaires	1			-						•
Placebo Script Review			X						X	Х	
MINI	X	X									
C-SSRS Baseline/ Screening Version		х									
C-SSRS- SLV Version			X	X	Xk	X	X	x	X	x	X
HAM-A (central rater)		X	X				X	x	X	X	X
MADRS (central rater)		X	X				X	x	X	x	X
CGI-S		X	X			X	X	X	X	X	X
CGI-I						X	X	X	X	X	X
PGI-S		X	X			X	X	X	X	X	X
PGI-C						X	X	X	X	X	X
SDS		X	X				X	X	X	X	X
EQ-5D-5L			X				X	X	X	X	X
PSQI			X						X	X	X
ASEX			X			v	X	X	X	X	X
Drug Effect VAS						X					
MEQ30						X					
SD-ASC						X					
blinding question						х					

CONFIDENTIAL

STUDY PERIOD	Optional Prescreen	SCREENING	BASELINE & DOSING				FOLLOW-UP				
Visit	Prescreen	Screening a	Baseline	Da Randomiza Dosing S	ay 1 ation (3A) & ession (3B)	Day 2	Week 1	Week 2	Week 4	Week 8	Week 12 (or Early WD)/EOS
Visit Number	N/A	1	2	3A	3B	4	5	6	7	8	9
Timing or Permitted Window	none	Up to 30 days prior to Baseline	1-5 days prior to Day 1 b, c	Pre- dose	Dosing & post- dose	1 day after dosing	Day 8 ±1 day	Day 15 ± 3 days	Day 29 ± 3 days	Day 57 ± 5 days	Day 85 ± 5 days
Dosing-Related Activities 											
Administration of study drug					Х						
Subject education / follow- up session with both DSMs			х	х		х	х	х			
Subject under observation by both DSMs					х						
Subject dosing day release from clinic/ Dosing Release Checklist					x						

5D-ASC: 5-Dimensional Altered States of Consciousness Rating Scale; AE: adverse event; ASEX: Arizona Sexual Experiences Questionnaire; AUDIT: Alcohol Use Disorders Identification Test; BP: blood pressure; BMI: body mass index; CGI-I: Clinical Global Impression – Improvement; CGI-S: Clinical Global Impression – Severity; C-SSRS (– SLV): Columbia-Suicide Severity Rating Scale (– Since Last Visit); DUDIT: Drug Use Disorders Identification Test; ECG: electrocardiogram; eCRF: electronic case report form; EOS: End of Study; ICF: informed consent form; MADRS: Montgomery-Åsberg Depression Rating Scale ; MEQ30: Mystical Experience Questionnaire; MINI: Mini-International Neuropsychiatric Interview; PGI-C: Patient Global Impression – Change; PGI-S: Patient Global Impression – Severity; PSQI: Pittsburgh Sleep Quality Index; SDS: Sheehan Disability Scale; HAM-A: Structured Interview Guide for the Hamilton Anxiety Rating Scale; THC: tetrahydrocannabinol; VAS, visual analogue scale; WD: Withdrawal

- a Screening (Visit 1) assessments may be performed over multiple days
- b If Baseline labs are needed, a minimum of 48 hours is required prior to Day 1 to allow for all eligibility assessment results to be reviewed to confirm subject eligibility
- c If the Baseline occurs within 14 days of Screening, Baseline labs are not required, and Dosing Session day (Visit 3B) may occur within 24 hours of the Baseline Visit
- d Sites should make an effort to obtain, at minimum, pharmacy records for subjects, and medical and /or psychiatric records
- vital signs should be performed prior to an ECG and/or a blood draw; Screening and Baseline vital signs require sitting, lying, and standing vital signs in order to capture orthostatic vitals.
- f On Day 1 (Visit 3A), the pre-dose vital signs (blood pressure, heart rate, respiration rate, and temperature) should be measured within 1 hour (+/- 15 mins) prior to study drug dosing. Note: Only BP and Temperature at Visit 3A will be used to confirm final eligibility against inclusion/exclusion criteria
- g Weight and height may be estimated during a remote Prescreen session but should be physically measured once the subject is on-site to determine eligibility
- h Safety laboratory assessments are optional at Week 1 (Visit 5) and Week 2 (Visit 6) unless values at the prior visit were clinically significant and warrant follow up

The Day 1/Dosing Session (Visit 3B) C-SSRS will be performed any time after 12 hours post dose and prior to the subject being released from the site

Refer to section 8.6 and the Dosing Session Monitor Manual for full details of subject education and follow-up sessions with DSMs

## **SAP Revisions**

Version 1.0 of the SAP was finalized at the time of Protocol version 6.0 (26Jul2023). The following table details the changes made to the SAP and/or addendum.

Protocol			
Version #	SAP		
Date	Section	Modification	Description and Rationale
1.0	All	Initial document	
Addendum	All	Initial Addendum document	Added safety and efficacy analysis after the Primary Efficacy Analysis was performed

## 1 INTRODUCTION

This statistical analysis plan (SAP) addendum describes the planned statistical analysis to be performed for the study, MMED008 entitled "A Phase 2, Multi-center, Randomized, Double-Blind, Parallel-Group, Dose-Finding Study to Assess the Effect of Four Doses of MM-120 for the Treatment of Anxiety Symptoms." has been engaged by Mind Medicine, Inc. (the 'sponsor') to develop the SAP and carry out the statistical analysis described in this SAP Addendum, including production of all tables, figures and listings.

This SAP addendum details statistical analyses that were added to the study after the unblinded review of the Primary Efficacy Endpoint. Thus, these analyses were not pre-planned in the protocol or SAP and are considered ad-hoc. This addendum contains no changes to the original pre-planned analyses contained in the final SAP, version 1.0 dated 01Aug2023.

